	
 • Visit 4- Treatment Visit • Visit 5- Treatment Visit • Follow-up telephone call
Study Products and Study Sequence	
Study Product: AM-301 Nasal Spray
 
Treatment groups will be as follows:
 
A: One Spray of AM-301 per nostril
 
B: Two Sprays of AM-301 per nostril (with different spray angles)
 
C: No treatment
 
The study will consist of 6 study sequences:
 
 • Sequence 1 (n = 6): ABC • Sequence 2 (n = 6): BCA • Sequence 3 (n = 6): CAB • Sequence 4 (n = 6): ACB • Sequence 5 (n = 6): BAC • Sequence 6 (n = 6): CBA
Study population	Approximately 36 males and non-pregnant females, 18-65 years of age inclusive, with a History of Perennial Allergic Rhinitis (PAR) due to house dust mites.
Route of Administration	Intranasal
Confinement	Study participants will remain confined to the clinic for approximately 4-5 hours during each screening and treatment EEC visits.
Study Conduct	
The clinical trial will consist of 5 clinic visits; (1 medical screening, 1 EEC screening visit 3 EEC treatment visits).
 
Medical Screening Visit 1 (Day-28 to -1) At Visit 1, eligible study participants will first sign the informed consent document, complete all screening procedures, including inclusion and exclusion criteria and safety labs, and move on to Visit 2 if eligible for EEC screening.
 
EEC Screening Visit 2 (Day 1) At Visit 2, eligible study participants will have a nasal exam performed by the Investigator. Study participants will then enter the EEC for a total of 3 hours. Study participants will record their symptoms every 20 ± 5 minutes throughout the 3-hour EEC session.
 
Treatment Visit 3 (Day 8 + 2), Visit 4 (Day 15 + 2) and Visit 5 (Day 22+ 2) Eligible study participants will return for Visit 3 after at least 7 days after visit 2. Study Participants will be randomized at Visit 3. Subsequently study participants will return to the clinic for Visit 4 at least 7 days after Visit 3 and for Visit 5 at least 7 days after Visit 4. Treatment will occur on site performed by trained clinical staff. Study participants will enter the EEC on these visits following administration, but no later than 10 minutes after

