	
treatment administration and will record their symptoms every 20 minutes throughout the 3-hour EEC session.
 
Following the assessments at Visit 5, this will conclude the study. AE's will also be recorded throughout each visit .
 
Follow-Up Telephone Call
 
Follow-up Telephone call will be done after approximately 7 + 2 days of completion of Visit 5.
 
The following assessment will be conducted:
 
 • Subjects will be asked for any occurrence of adverse events after last treatment administration. • Subjects will be asked if they have taken any concomitant medications since last treatment administration.

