
	
18. Subject has a positive result for SARS-CoV-2 and/ or has clinical signs and symptoms consistent with COVID-19 infection, e.g., fever, dry cough, dyspnea, sore throat, fatigue, muscle or body aches and gastrointestinal symptoms or confirmed infection by appropriate SARS-CoV-2PCR test within the 2 weeks prior to visit 1.
 
19. Study participants who have taken COVID-19 Vaccine 3 days or less prior to a visit.
 
20. Study participants that have a relationship dependency with the Sponsor or study site staff.

Statistical Analysis	
For applicable endpoints, the treatment comparison between treated and non-treated will be performed using a mixed-effects Analysis of Covariance Model (ANCOVA) for a crossover study for 3 periods. The model will include Treatment, Period (Visit) and Sequence as fixed effects, baseline (pre-dose) measurement as a covariate. Subject nested within treatment sequence will be fitted as a random effect. LS means and SEs by treatment arm will be extracted from the model and presented. Further, contrasts between LS means will be extracted for (i) (1-spray+2-sprays)/2 vs no treatment (ii) 1-spray vs no treatment and (iii) 2-sprays vs no treatment. The 95% CI and 2-sided p-values will be provided for each of these contrasts.
 
Appropriate statistical analysis will be performed to analyze the global rating scales for efficacy and tolerability.
 
Safety Population: All study participants who are randomized will be included in the Safety population.
 
Intent to Treat (ITT) Population: All study participants in the Safety Population who provide at least one TNSS assessment will be included in ITT population.
 
Per Protocol (PP) Population: PP Population will include all study participants in ITT who completed the study and do not have any major protocol violations.
 
The analyses of all efficacy endpoints will be carried out using the ITT population. Supportive analyses will also be provided for the primary endpoint using the PP population.

Safety Analysis	Safety analysis will include descriptive analysis and listings according to received treatment.

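### Are adverse events at home after each participant's first AM-301 administration left unasked?

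*Combined protocol and SAP*

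**What the plan says.** Three places in the Study Summary (section 4) bear on this.

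- **Study Conduct** covers the visits: "AE's will also be recorded throughout each visit". Time on site is short: "Study participants will remain confined to the clinic for approximately 4-5 hours during each screening and treatment EEC visits".
- **Follow-Up Telephone Call** covers the end of the study: "Follow-up Telephone call will be done after approximately 7 + 2 days of completion of Visit 5". Two questions are listed: "Subjects will be asked for any occurrence of adverse events after last treatment administration" and "Subjects will be asked if they have taken any concomitant medications since last treatment administration".
- **Safety Analysis** says how the events are reported: "Safety analysis will include descriptive analysis and listings according to received treatment".

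The summary mentions no diary, no interim call and no explicit question at Visit 4 or 5 about the time since the visit before. It also does not say whether the final administration means Visit 5 or the last AM-301 dose. The two differ for the sequences that end with no treatment.

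**The concern.** Occurrence and severity of adverse events is a safety endpoint in a study described as pivotal. Participants spend a few hours in the clinic and then at least a week at home before the next challenge. The plan spells out a question about home events for the time after the final administration and for no earlier interval.

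Taken literally, the length of follow-up after a dose would depend on its place in the sequence: days for the last dose, hours for the first. Summaries by treatment would then mix short and long windows, and a reaction that appeared at home after first exposure could go unrecorded.

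The medication question has the same limit. Medication taken between challenges could affect the next TNSS, and exclusion criterion 2 turns on medication that might influence an EEC session.

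**Working it through.** The plan gives no figure on this point, so there is none to reproduce. The stated sample size and power do not depend on it. The check has two parts: a count by sequence, then a reading of the sentences together.

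**Inputs.** The summary states that "The study will consist of 6 study sequences", with six participants each. A is one spray per nostril, B is two sprays, C is no treatment. Nominal days are 8, 15 and 22 for Visits 3, 4 and 5, each with a window of +2 days and at least 7 days between visits. The call comes 7 days (+2) after Visit 5, nominally Day 22 + 7 = Day 29.

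**Count by sequence.** Each sequence contains A and B once, so there are 36 × 2 = 72 planned AM-301 administrations.

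| Sequence | First AM-301 | Last AM-301 | Nominal days between |
|---|---|---|---|
| ABC | A, Visit 3 | B, Visit 4 | 15 − 8 = 7 |
| BAC | B, Visit 3 | A, Visit 4 | 15 − 8 = 7 |
| CAB | A, Visit 4 | B, Visit 5 | 22 − 15 = 7 |
| CBA | B, Visit 4 | A, Visit 5 | 22 − 15 = 7 |
| BCA | B, Visit 3 | A, Visit 5 | 22 − 8 = 14 |
| ACB | A, Visit 3 | B, Visit 5 | 22 − 8 = 14 |

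**Strict reading, call counted from the last AM-301 dose.**
- Prompted at-home coverage: 36 of 72 administrations (50%).
- One spray is last in BCA, BAC and CBA: 3 × 6 = 18 of 36.
- Two sprays are last in ABC, CAB and ACB: 3 × 6 = 18 of 36.
- No treatment falls at Visit 5 in ABC and BAC: 2 × 6 = 12 of 36.
- The look-back is 29 − 15 = 14 days when the last dose is at Visit 4 and 29 − 22 = 7 days otherwise. Each regimen has 6 participants with 14 days and 12 with 7 days, so the lengths balance too.

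**Strict reading, call counted from Visit 5.**
- One spray at Visit 5 (BCA, CBA): 12 of 36. Two sprays (CAB, ACB): 12 of 36. No treatment (ABC, BAC): 12 of 36.
- AM-301 administrations covered: 24 of 72 (33%), leaving 48.

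**Reading the sentences together.** Both strict readings assume that Visits 4 and 5 yield nothing about the interval before them. The text does not say so. The visit sentence states when recording takes place and sets no condition on when an event started. An event that began at home after Visit 3 and is reported at Visit 4 is therefore recorded at a visit, as the sentence provides. Only the interval after Visit 5 has no later visit, and the call fills it. Its timing of 7 + 2 days matches the spacing of the visits.

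If Visits 4 and 5 cover what precedes them, the windows are Visit 3 to 4, Visit 4 to 5 and Visit 5 to call. Each is 7 days nominally and at most 9: 15 + 2 − 8 = 9, 22 + 2 − 15 = 9, and 7 + 2 = 9. Coverage is then 36 of 36 for each of A, B and C.

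**Other safeguards.** Patient and investigator tolerability ratings for single and double application are safety endpoints at the treatment visits, so acute tolerability is assessed after the first AM-301 administration as well. For medication, exclusion criterion 2 calls for an investigator's judgement about the EEC session, which presupposes some enquiry. The model adjusts for the pre-dose score, and the per-protocol analysis removes major violations. These do not replace a medication question, but they do not leave the matter untouched.

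**The case for a change.** The best argument for a change is that the plan writes a question for the last interval and none for the earlier ones. A volunteered report is weaker than a solicited one, and first exposure is when intolerance would first show. If the call counts from the last AM-301 dose, no treatment has coverage of 12 of 36 against 18 of 36 for each spray regimen. In ABC and BAC the call then spans an AM-301 interval and a no-treatment interval, with no stated rule for attributing events. Writing the question down would cost almost nothing.

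Part of this stands. The summary is silent on the question, the final administration has two possible meanings, and a site that noted only volunteered events could under-count.

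The rest does not follow. The text does not limit recording to events that begin in the clinic, so it does not show that home events would be missed. The analysis is descriptive with listings: no adverse event rate, test or equal-follow-up assumption is stated. The 18 against 12 contrast needs both the strict reading and one of the two meanings. The text at hand is also a study summary, where the wording of such questions is commonly compressed, so silence there is weak evidence of a defect in design.

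**Conclusion.** No change follows. This is a gap in detail that site staff and analysts can fill sensibly: ask at Visits 4 and 5 what happened since the last visit, and assign the event to the period in which it began. No stated rule has been shown to give a wrong result.

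If no one asked at Visits 4 and 5, 36 to 48 of the 72 AM-301 administrations would rely on spontaneous report of home events. That risks some under-counting, equal for one and two sprays, in a descriptive summary. On the ordinary reading, all three treatments have the same window of 7 to 9 days.

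The conclusion assumes six participants per sequence, visits close to schedule, and staff who record events reported to them at a visit. About 30 of 36 are expected to complete, so the balance would be approximate in practice. That staff will ask is a judgement about ordinary conduct; the documents do not state it.

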Sample Size Determination	It is hypothesized that the Total Nasal Symptom Score (TNSS) over 180 min post treatment with no treatment is 2.3 units as compared to 1.0 and 1.6 units for, respectively, 2-sprays and 1-spray of AM-301. Assuming the SD of the within subject change is 2 units, N=30 randomized subjects will provide 87.4% power at the 2-sided 5% alpha level to test the hypothesis that the TNSS score averaged across 1-spray and 2-sprays is superior to no treatment. Sufficient numbers of volunteers will be screened to randomize approximately 36 study participants to have 30 completed study participants.

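### Does a Safety population of all randomized participants dilute the adverse-event rates for AM-301?

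*Combined protocol and SAP*

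**What the plan says.** All of the relevant text is in section 4, Study Summary.

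- **Statistical Analysis, Safety population:** "All study participants who are randomized will be included in the Safety population". No exposure condition is attached.
- **Statistical Analysis, ITT population:** "All study participants in the Safety Population who provide at least one TNSS assessment will be included in ITT population". ITT is therefore a subset of Safety.
- **Safety Analysis:** "Safety analysis will include descriptive analysis and listings according to received treatment". No formal test, threshold or adverse-event rate is given, and the denominator for percentages is not spelled out.
- **Study Products and Study Sequence:** one of the three conditions is "C: No treatment". There are six sequences of six participants. Two of them, CAB and CBA, begin with the untreated period (for example "Sequence 3 (n = 6): CAB").
- **Study Conduct:** "Study Participants will be randomized at Visit 3", which is the first treatment visit, and "Treatment will occur on site performed by trained clinical staff".
- **Sample Size Determination:** the aim is to "randomize approximately 36 study participants to have 30 completed study participants".

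**The concern.** A safety set for a device is usually expected to contain people who were exposed to it. Here a participant in CAB or CBA who withdraws after the first period has had only an untreated chamber challenge, yet belongs to the Safety population. More generally, anyone who leaves early has missed at least one of the three conditions. The plan itself allows for about six non-completers.

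If a programmer took the size of the Safety population as the denominator in each treatment column, events would be counted only among people who received the regimen but divided by a number that includes people who did not. Absolute adverse-event rates for one and two sprays would come out too low, which flatters the device. Adverse events are a named safety endpoint of a study labelled pivotal, and with 36 participants a few people move a percentage visibly. Nesting ITT inside Safety adds a second worry: a weakness in one definition could carry over to the other.

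**Working it through.** **Inputs.** Randomized: 36 (6 sequences × 6). Completers planned: 30 (Sample Size Determination). Planned dropouts: 36 − 30 = 6. The plan gives no adverse-event rate and no safety sample size, so there is no safety figure to reproduce. The stated power concerns TNSS and has no bearing here. The 20% rate below is an assumption for illustration.

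**Formula.** If every column were divided by 36, then

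reported rate = true rate among the exposed × (number exposed ÷ 36).

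**How many are exposed to a given condition?** Across the sequences ABC, BCA, CAB, ACB, BAC and CBA, each condition occurs exactly twice in each period. Take one dropout per sequence.

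- All six leave after period 1: two have already had the condition and four miss it, so 36 − 4 = 32 are exposed.
- Three leave after period 1 and three after period 2, spread evenly: on average 3 × 4/6 + 3 × 2/6 = 3 miss it, so 33 are exposed.
- All six leave after period 2: two miss it, so 34 are exposed.
- Extreme case, all six miss the same condition: 30 are exposed.

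| Pattern of six dropouts | Exposed ÷ 36 | Relative understatement | A true 20% reads |
|---|---|---|---|
| Even, all after period 2 | 34/36 = 0.944 | 5.6% | 18.9% |
| Even, half after each period | 33/36 = 0.917 | 8.3% | 18.3% |
| Even, all after period 1 | 32/36 = 0.889 | 11.1% | 17.8% |
| All miss the same regimen | 30/36 = 0.833 | 16.7% | 16.7% |
| Received-treatment denominators | 1.000 | 0 | 20.0% |

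**Never exposed to AM-301 at all.** Leaving aside withdrawal before period 1, these people come only from CAB and CBA, which hold 12 of 36. If six leave after period 1 and are spread evenly, that is 6 × 12/36 = 2 people.

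**Zero events.** The exact one-sided 95% upper bound is 1 − 0.05^(1/n): 9.5% for n = 30 and 8.0% for n = 36.

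**Effect on the comparison.** A denominator of 36 would apply to the no-treatment column too. With even dropout all three columns shrink by the same factor. The ratio of device to no-treatment rates is unchanged, and absolute rates and their differences shrink by that factor.

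**Which denominator does the plan imply?** The Safety population rule says whose data are kept. The Safety Analysis rule says how they are arranged: by treatment received. A person who never had two sprays has no place in a two-spray column arranged that way, either as an event or as a person at risk. Nothing in the document makes 36 the denominator of each column.

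**Would redefining the sets help?** Take a CAB participant who withdraws after period 1.

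- Requiring at least one AM-301 application removes this person, and with them any adverse event from the untreated challenge. A no-treatment column based on everyone who had that period needs the same person. The two rules conflict.
- The requirement also leaves regimen denominators uncorrected: someone who had only one spray per nostril stays in the set when two sprays are tabulated.
- Defining ITT directly from randomized participants changes nobody, because Safety already equals all randomized. The nesting would do harm only if Safety were narrowed.

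**The case for a change.** The strongest case for acting is that the sentence on treatment received assigns events to conditions but never names the number to divide by. A programmer could take the population count as the header of every column. This is easier to do in a crossover than in a parallel trial, because every participant is nominally assigned to every condition. The study is small and labelled pivotal, adverse events are a stated endpoint, and one sentence would remove the doubt. Randomization at the first treatment visit with staff-administered dosing makes withdrawal before period 1 unlikely, but it does not prevent withdrawal between visits.

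Part of this stands: the denominator is not written down, and a population count in every column would lower absolute rates. It does not show that the plan directs such a count. A table arranged by treatment received ordinarily carries the number who received each treatment, and that number is available from the on-site dosing records. The claim of bias in the device's favour is also incomplete, because the same divisor would lower the no-treatment rate.

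**Conclusion.** The concern does not call for a change. The Safety definition has no exposure condition, but safety is reported by treatment received, and on the natural reading the dilution is zero. The gap is a missing detail in a descriptive analysis: the number at risk in each column, which analysts would take as those who entered that period and received that condition. Were 36 used throughout, six evenly spread dropouts would understate absolute rates by about 6% to 11% in relative terms. The 17% figure needs all six to miss the same regimen. These sizes assume that dropout stays at the planned six. No stated test or decision depends on them.

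Keeping all randomized participants in the Safety set has a positive merit here, since it retains adverse events from people who had only the untreated challenge. Narrowing the set would lose those events without correcting the regimen denominators, and detaching ITT from Safety would alter no one's membership.
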